### 8.3 Study procedures

#### *Inclusion*

The study is conducted in healthy volunteers without gastrointestinal complaints and unremarkable medical history. Volunteers are recruited by distribution of patient information folders, containing study information and the investigators contact information, at the gastroenterology and Hepatology outpatient clinics of Erasmus MC University Medical Center and Franciscus Gasthuis & Vlietland. When volunteers contact the investigator the study outline is discussed and inclusion and exclusion criteria are checked. Volunteers are asked whether they have a medical history or are currently experiencing any complaints, they do not undergo additional tests or check-ups to ensure they are healthy. When a healthy volunteer decides to participate in the study an Informed Consent Form will be signed.

Volunteers will be randomized and assigned to one of four study groups.

### *Control*

Two different control groups both consisting of 5 volunteers will be used during the study. The first group will receive  $^{13}\text{C}$ -butyrate and the second group  $^{13}\text{C}$ -glucose. The control groups will perform the breath tests without performing any physical exercise.

### *Intervention*

Two different intervention groups both consisting of 5 volunteers will be used during the study. The first group will receive  $^{13}\text{C}$ -butyrate and the second group  $^{13}\text{C}$ -glucose. All intervention groups will be performing a standardized bicycle ergometer exercise test with a total duration of 30 minutes(12). The exercise test has been proven to elicit mesenteric ischemia in athletes. Previous studies suggest an additional 10 minute period of splanchnic hypo perfusion after discontinuation of exercise(13, 14).

The exercise test consist of 3 phases.

- Phase 1: The first 10 minutes of exercise are used to gradually increase the workload until submaximal exercise intensity is reached. Submaximal exercise is defined as lactate between 3 and 5.5 mmol/L. Lactate measurements are performed every 2 minutes, using a rapid lactate measurement kit.
- Phase 2: From minute 10 until 20 submaximal exercise intensity is maintained by adjusting the workload based on lactate measurements. The lactate measurements are performed every 3 minutes.
- Phase 3: Minute 20 until 30 are used to reach maximal exercise intensity. Every 3 minutes the workload is increased by 10% of the submaximal workload until exhaustion. Lactate measurements will be continued with 3 minute intervals.

All volunteers will be instructed to take their last meal 6 hours before start of the breath test.

Volunteers in the  $^{13}\text{C}$ -butyrate group receive an oral dose of 0.03  $\mu\text{mol}$   $^{13}\text{C}$ -butyrate(10).

Volunteers in the  $^{13}\text{C}$ -glucose group receive an oral dose 20 mmol  $^{13}\text{C}$ -glucose.

### *Randomisation*

Allocation to the  $^{13}\text{C}$ -butyrate and  $^{13}\text{C}$ -glucose group and allocation to the control or intervention group will be performed by randomisation. Blinding of the healthy volunteers will not be possible, since the intervention group has to perform an exercise test.

### *Breath test*

Both intervention and control group will perform breath tests at the following time points baseline, 0.5, 1, 1.25 1.5, 1.75, 2, 2.25, 2.5, 3, 3.5 and 4 hours after ingestion of  $^{13}\text{C}$ -butyrate

or  $^{13}\text{C}$ -glucose. Two breath samples are collected at all mentioned time points. The decision to perform breath testing for a total of 4 hours was based on a study that determined  $^{14}\text{CO}_2$  elimination patterns after instillation of butyrate in human caecum and a study describing  $^{13}\text{CO}_2$  elimination patterns in healthy volunteers (10, 15). The tracer could be measured in exhaled air at the first time point, which was 30 minutes after instillation. A peak in expired  $^{14}\text{CO}_2$  was measured after 2 hours. Four hours after instillation approximately 55% of the total  $^{14}\text{CO}_2$  dose had been expired, 24 hours after instillation 70% of the instilled dose had been expired. Since we are interested in the peak of expired  $^{13}\text{CO}_2$  a measurement period of 4 hours seems sufficient, even in the intervention group, in whom a delayed or lower peak is expected. The frequency of breath testing is intensified between 1 and 2.5 hours after ingestion, in order to detect the timing of the  $^{13}\text{CO}_2$  peak more precisely.

#### *Follow-up*

There is no follow-up of healthy volunteers.

Study procedures	Control group	Intervention group
Oral dose of either 0.03 $\mu\text{mol}$ $^{13}\text{C}$ -butyrate or 20 mmol $^{13}\text{C}$ -glucose	Yes	Yes
Insertion of venous canule (measurement of lactate, 2 serum samples: 1 at baseline and 1 after the exercise test)	No	Yes
Bicycle ergometer exercise test	No	Yes
Collection of 2 breath samples at baseline, 0.5, 1, 1.25, 1.5, 1.75, 2, 2.25, 2.5, 3, 3.5 and 4 hours after ingestion of $^{13}\text{C}$ -butyrate or $^{13}\text{C}$ -glucose	Yes	Yes

#### *Analysis of breath samples*

Measurement of  $^{13}\text{CO}_2$  will be performed using mass spectrometry (IDMicro Breath, Compact Science Systems, Newcastle-Under-Lyme, United Kingdom). The mass spectrometry procedure is equal to the procedures used to measure  $^{13}\text{CO}_2$  in testing for Helicobacter Pylori, which is current clinical practice.

#### **8.4 Withdrawal of individual subjects**

Subjects can leave the study at any time for any reason if they wish to do so without any consequences. The investigator can decide to withdraw a subject from the study for urgent medical reasons.

**8.4.1 Specific criteria for withdrawal (if applicable)**

Not applicable

**8.5 Replacement of individual subjects after withdrawal**

Inclusion will end after inclusion of 5 volunteers in each of the four groups.

**8.6 Follow-up of subjects withdrawn from treatment**

Follow-up is not performed.

**8.7 Premature termination of the study**

The study will be terminated prematurely when participation is associated with serious health risks, which are not expected.

## 9 SAFETY REPORTING

### 9.1 Temporary halt for reasons of subject safety

In accordance to section 10, subsection 4, of the WMO, the sponsor will suspend the study if there is sufficient ground that continuation of the study will jeopardise subject health or safety. The sponsor will notify the accredited METC without undue delay of a temporary halt including the reason for such an action. The study will be suspended pending a further positive decision by the accredited METC. The investigator will take care that all subjects are kept informed.

### 9.2 AEs, SAEs and SUSARs

#### 9.2.1 Adverse events (AEs)

Adverse events are defined as an undesirable experience occurring to a subject during the study, related to the study. All adverse events reported spontaneously by the subject or observed by the investigator or his staff will be recorded.

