### *Intervention*

Two different intervention groups both consisting of 5 volunteers will be used during the study. The first group will receive  $^{13}\text{C}$ -butyrate, the second group  $^{13}\text{C}$ -glucose. All intervention groups will be performing a standardized bicycle ergometer exercise test with a total duration

of 30 minutes(12). The exercise test has been proven to elicit mesenteric ischemia in athletes. Previous studies suggest an additional 10 minute period of splanchnic hypo perfusion after discontinuation of exercise(13, 14).

The exercise test consist of 3 phases.

- Phase 1: The first 10 minutes of exercise are used to gradually increase the workload until submaximal exercise intensity is reached. Submaximal exercise is defined as lactate between 3 and 5.5 mmol/L. Lactate measurements are performed every 2 minutes, using a rapid lactate measurement kit.
- Phase 2: From minute 10 until 20 submaximal exercise intensity is maintained by adjusting the workload based on lactate measurements. The lactate measurements are performed every 3 minutes.
- Phase 3: Minute 20 until 30 are used to reach maximal exercise intensity. Every 3 minutes the workload is increased by 10% of the submaximal workload until exhaustion. Lactate measurements will be continued with 3 minute intervals.

[figure not shown]

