### 8.2 Randomisation, blinding and treatment allocation

Participating volunteers will not be blinded. Randomization will be performed into four groups of five volunteers.

Randomisation will be performed through a random list generated by an online randomisation tool and is executed by a person not actively involved in the study. The randomisation tool can be found at <https://www.sealedenvelope.com/simple-randomiser/v1/lists>. The used seed will be noted and saved, the treatment groups are: BC, BI, GC, GI. Block sizes will be 5 blocks of 4, resulting in a randomized list of 20 subjects (5 per group). The created list will be saved and used to fill 20 envelopes numbered 1-20. Each envelope will contain the treatment group as specified in the randomly generated list. Envelope 1 will be for the first subject enrolled in the study, envelope 2 for the second subject enrolled in the study, etc.

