#### 9.2.2 Serious adverse events (SAEs)

A serious adverse event is any untoward medical occurrence or effect that

- results in death;
- is life threatening (at the time of the event);
- requires hospitalisation or prolongation of existing inpatients' hospitalisation;
- results in persistent or significant disability or incapacity;
- is a congenital anomaly or birth defect; or
- any other important medical event that did not result in any of the outcomes listed above due to medical or surgical intervention but could have been based upon appropriate judgement by the investigator.

An elective hospital admission will not be considered as a serious adverse event.

The sponsor will report the SAEs through the web portal *ToetsingOnline* to the accredited METC that approved the protocol, within 7 days of first knowledge for SAEs that result in death or are life threatening followed by a period of maximum of 8 days to complete the initial preliminary report. All other SAEs will be reported within a period of maximum 15 days after the sponsor has first knowledge of the serious adverse events.

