### **9.4 Follow-up of adverse events**

All AEs will be followed until they have abated, or until a stable situation has been reached. Depending on the event, follow up may require additional tests or medical procedures as indicated, and/or referral to the general physician or a medical specialist. SAEs need to be reported till end of study within the Netherlands, as defined in the protocol

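### Section 9.2.1 makes relatedness part of the adverse event definition, so non-serious events judged unrelated need not be recorded or followed, and serious events are no longer a subset of adverse events

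*Combined protocol and SAP*

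**What the plan says.** Section 9.2.1 defines the term with a causal condition: "Adverse events are defined as an undesirable experience occurring to a subject during the study, related to the study". It then sets the recording rule: "All adverse events reported spontaneously by the subject or observed by the investigator or his staff will be recorded".

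Section 9.2.2 opens its definition differently: "A serious adverse event is any untoward medical occurrence or effect that" meets one of the listed seriousness criteria. Its reporting rule carries no causal condition either. Fatal or life-threatening events go to the ethics committee within 7 days, and for the rest: "All other SAEs will be reported within a period of maximum 15 days after the sponsor has first knowledge of the serious adverse events".

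Section 9.4 sets the follow-up duty: "All AEs will be followed until they have abated, or until a stable situation has been reached".

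On the setting, section 8.2 says: "Randomization will be performed into four groups of five volunteers". Two of these groups do the exercise test, whose third phase is described under Intervention (sections 3, 5.1 and 8.3): "Every 3 minutes the workload is increased by 10% of the submaximal workload until exhaustion". Section 8.2 also says that volunteers are not blinded.

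On withdrawn subjects, section 8.6 says: "Follow-up is not performed".

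**The concern.** Relatedness is normally an attribute assigned to an event once it has been written down. Here it is a condition for being an adverse event at all, so an event judged unrelated falls outside the recording rule. An event that was never recorded cannot be reassessed if a similar one appears later in another volunteer.

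The setting gives this some weight. Half the volunteers exercise to exhaustion in a test meant to induce temporary mesenteric ischemia. Their health is established by asking about history and complaints, without additional tests (section 3, Inclusion). The Summary says that no adverse events are expected. Sections 9.5 (safety board) and 12.2 (monitoring) are both marked not applicable, so the protocol describes no independent check that would pick up an omitted event. At stake is the completeness of the safety record, not the breath-test result.

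**Working it through.** The protocol states no figure on this point, so the check is a comparison of the wording.

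**Inputs**
- AE definition and recording rule: section 9.2.1.
- SAE definition and reporting rule: section 9.2.2.
- Follow-up rule: section 9.4.
- Group sizes: section 8.2, four groups of 5, so 4 × 5 = 20 volunteers. The two exercise groups give 2 × 5 = 10, and 10/20 is one half.

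**Step 1: what each rule reaches.** Every AE under 9.2.1 is related by definition. An SAE under 9.2.2 may be related or unrelated. Crossing the two attributes gives four kinds of event:

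| Event | AE under 9.2.1, so recorded | SAE under 9.2.2, so reported | Follow-up under 9.4 |
|---|---|---|---|
| Related, serious | Yes | Yes | Yes |
| Related, non-serious | Yes | No | Yes |
| Unrelated, serious | No | Yes | Unclear: the duty is worded for AEs |
| Unrelated, non-serious | No | No | No |

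**Step 2: consistency.** The third row is an SAE that is not an AE. SAEs are therefore not a subset of AEs, and 9.2.1 and 9.2.2 are inconsistent in scope.

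**Step 3: the gap.** Only the fourth row has no requirement of any kind.

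**Step 4: does another section close it?** The annual progress report (12.4) asks for serious events and reactions only. The endpoint sections (8.1.1 to 8.1.3) and section 10 contain nothing on adverse events. The abbreviation list has separate entries for adverse event and adverse reaction, but does not define either. No section requires an event to be recorded regardless of cause, and none says who judges relatedness or by what criteria.

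**Step 5: size.** The documents give no rate of non-serious events and no share likely to be judged unrelated, so the number lost cannot be estimated.

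**Step 6: sections 8.6 and 9.4.** Section 8.4 allows the investigator to withdraw a subject for urgent medical reasons. Section 8.6 then provides no follow-up after withdrawal, while 9.4 requires adverse events to be followed. The text does not say how the two apply together to a volunteer withdrawn with an unresolved event.

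**The case against.** The case on the other side is substantial, and much of it stands.

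- **No serious event is lost.** Section 9.2.2 has no causal condition and requires reporting within 7 or 15 days. This stands. A reader might infer from 9.2.1 that all events judged unrelated go uncaptured, but 9.2.2 contradicts that for serious ones.
- **The condition is relatedness to the study, not to the tracer.** It can cover exercise, the cannula, fasting and breath sampling, and an event straight after exhaustive exercise is among the likeliest to be judged related. This is fair, and it makes the loss of an obvious exercise injury unlikely. It does not help with ambiguous complaints, because no criteria are given.
- **Bias between arms is not shown.** A reader might infer that exercise and resting arms would be recorded selectively. The documents give no direction: staff could attribute more complaints to the study in exercisers, or dismiss them as ordinary exertion. The documents state only that volunteers are unblinded; they are silent on whoever would judge relatedness.
- **No comparison of adverse events is planned.** Safety is not an endpoint, and section 10 has no adverse event analysis. A reader might also infer that this comparison would be the only evidence on the safety of the exercise test in these volunteers. That goes too far, since SAE reports and recorded related events remain.
- **Section 9.4 can be read as the specific rule for adverse events, alongside a general absence of study follow-up in 8.6.** That reading is available, so the pair is an ambiguity and not a demonstrated contradiction.

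None of this supplies a recording requirement for a non-serious event judged unrelated.

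**Conclusion.** The point holds in limited form. Sections 9.2.1 and 9.2.2 differ in scope, and non-serious events judged unrelated have no recording requirement (9.2.1) and no follow-up requirement (9.4). This comes from a rule the protocol states, not from a detail left out. The judgement that decides inclusion has no stated criteria or assessor.

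The rule applies to all 20 volunteers, of whom 10 exercise to exhaustion. The number of events affected is unknown and may be small. The breath-test endpoints, their analysis and the sample size are not touched.

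The conclusion assumes that the recording and follow-up rules use the term adverse event as 9.2.1 defines it. If staff in practice record everything and judge relatedness afterwards, nothing is lost, but the protocol does not ask them to. The wording of 8.6 against 9.4 is a minor point of clarification.

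**What to change.** In section 9.2.1, define an adverse event as any undesirable experience occurring to a subject during the study, whether or not considered related to the study procedures. Record relatedness as a separate field for each event, and state who assesses it and by what criteria. SAEs then become a subset of AEs, and 9.4 reaches every event without further change.

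As a minor clarification, reconcile 8.6 with 9.4 so that the text says how they apply together to a volunteer withdrawn with an unresolved event.

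The cost is a changed sentence and a short addition in 9.2.1, one clarifying sentence in 8.6, and a few more non-serious entries in 20 volunteers. No endpoint, analysis or sample size changes.

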#### 9.2.2 Serious adverse events (SAEs)

A serious adverse event is any untoward medical occurrence or effect that

- results in death;
- is life threatening (at the time of the event);
- requires hospitalisation or prolongation of existing inpatients' hospitalisation;
- results in persistent or significant disability or incapacity;
- is a congenital anomaly or birth defect; or
- any other important medical event that did not result in any of the outcomes listed above due to medical or surgical intervention but could have been based upon appropriate judgement by the investigator.

An elective hospital admission will not be considered as a serious adverse event.

The sponsor will report the SAEs through the web portal *ToetsingOnline* to the accredited METC that approved the protocol, within 7 days of first knowledge for SAEs that result in death or are life threatening followed by a period of maximum of 8 days to complete the initial preliminary report. All other SAEs will be reported within a period of maximum 15 days after the sponsor has first knowledge of the serious adverse events.

### **9.2.3 Suspected unexpected serious adverse reactions (SU-SARs)**

Not applicable.

### **9.3 Annual safety report**

Not applicable

### **9.4 Follow-up of adverse events**

All AEs will be followed until they have abated, or until a stable situation has been reached. Depending on the event, follow up may require additional tests or medical procedures as indicated, and/or referral to the general physician or a medical specialist. SAEs need to be reported till end of study within the Netherlands, as defined in the protocol

### **9.5 [Data Safety Monitoring Board (DSMB) / Safety Committee]**

Not applicable

## 10 STATISTICAL ANALYSIS

Baseline characteristics of the intervention and control group will be shown and compared. Categorical data is compared by chi-square or Fisher exact testing. Numerical data is shown as mean and standard deviation or median and interquartile range. Comparison of the numerical data of intervention and control group will be performed by the independent sample t-test or the Mann-Whitney-U test.

### 10.1 Primary study parameter(s)

The height of the  $^{13}\text{CO}_2$  peak of the intervention and control groups will be compared by the independent sample t-test or Mann-Whitney-U test. Repeated measurement correction will be performed with the Bonferroni method. The area under the  $^{13}\text{CO}_2$  curves will be compared by the independent sample t-test or Mann-Whitney-U test.

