## 2. OBJECTIVES

Primary Objective:

To explore the possibility of detecting mesenteric ischemia by  $^{13}\text{C}$ -butyrate and  $^{13}\text{C}$ -glucose breath testing by comparing timing and concentration of the peak of expired  $^{13}\text{CO}_2$ .

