#### *Breath test*

Both intervention and control group will perform breath tests at the following time points baseline, 0.5, 1, 1.25 1.5, 1.75, 2, 2.25, 2.5, 3, 3.5 and 4 hours after ingestion of  $^{13}\text{C}$ -butyrate or  $^{13}\text{C}$ -glucose (figure 1). A breath sample is obtained by blowing a single breath of air through a straw into a test tube. Two breath samples are collected at all mentioned time points. The decision to perform breath testing for a total of 4 hours was based on a study that determined  $^{14}\text{CO}_2$  elimination patterns after instillation of butyrate in human caecum and a study describing  $^{13}\text{CO}_2$  elimination patterns in healthy volunteers(10, 15). The tracer could be measured in exhaled air at the first time point, which was 30 minutes after instillation. A peak in expired  $^{14}\text{CO}_2$  was measured after 2 hours. Four hours after instillation approximately 55% of the total  $^{14}\text{CO}_2$  dose had been expired, 24 hours after instillation 70% of the instilled dose had been expired. Since we are interested in the peak of expired  $^{13}\text{CO}_2$  a measurement period of 4 hours seems sufficient, even in the intervention group, in whom a delayed or lower peak is expected. The frequency of breath testing is intensified between 1 and 2.5 hours after ingestion, in order to detect the timing of the  $^{13}\text{CO}_2$  peak more precisely.

Figure 1. timeline collection of breath samples.

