### **d. Sample size calculation**

This study is a proof of principal study, no previous studies exist on this topic, therefore a sample size calculation could not be performed. We have chosen to include a total of 20 healthy volunteers in order to be able to compare 5 control subjects and 5 intervention

subjects for each breath test. In case the number of 5 subjects per group is insufficient to detect a statistical difference, the generated data can be used to perform a sample size calculation for a second study.

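### Section 10.1's Bonferroni repeated-measurement correction matches no planned comparison, and the comparisons it should cover are not listed

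*Combined protocol and SAP*

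**What the plan says.** Section 10.1 has three sentences on the primary analysis. The height of the "peak of the intervention and control groups will be compared by the independent sample t-test or Mann-Whitney-U test". Next comes: "Repeated measurement correction will be performed with the Bonferroni method". Then the area under the "curves will be compared by the independent sample t-test or Mann-Whitney-U test". Sections 10.2 to 10.4 are marked not applicable, and no part of Section 10 describes a test at single breath-test times or a repeated-measures model.

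Section 4d sets the comparison for each breath test: 20 volunteers were chosen "in order to be able to compare 5 control subjects and 5 intervention" subjects. It gives no alpha, effect size or power.

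The design does repeat measurements in two ways. The procedures table in Section 8.3 lists "Collection of 2 breath samples at baseline, 0.5, 1, 1.25, 1.5, 1.75, 2, 2.25, 2.5, 3, 3.5 and 4 hours after ingestion", which is 12 times, 11 of them after ingestion. Section 3 (Breath test) adds: "Two breath samples are collected at all mentioned time points".

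Section 2 gives the objective as "comparing timing and concentration of the peak of expired" labelled carbon dioxide. Peak timing has no test in Section 10.1.

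**The concern.** Peak height and AUC each reduce a volunteer's curve to a single number, and two independent groups are then compared on that number. Such a comparison contains no repeated measurement to correct for. An analyst following Section 10.1 must therefore guess what the correction covers. It could be the two tracers, the two or three curve features, both together, or the sampling times. The guess sets k, and k decides whether the same data count as significant. Because the choice could be made after the data are seen, the plan does not fix its own primary test. With five per group there is little power to lose.

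**Working it through.** **Inputs.** Group size is 5 v 5 per tracer (Section 4d, and the randomisation list in Section 8.2: 5 blocks of 4 = 20, 5 per group). The tests are t-test or Mann-Whitney (Section 10.1). There are 12 sampling times, 11 after ingestion (Section 8.3 table). The plan states no alpha, corrected alpha, k or power, so there is no figure to reproduce. Assumed here: familywise alpha 0.05, two-sided unless stated, and a standardised difference d shown over a range.

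**Possible k.** One outcome over two tracers, or two outcomes in one tracer: 2. Three outcomes (with peak timing) in one tracer: 3. Two outcomes x two tracers: 4. Three x two: 6. Sampling times, one tracer: 11 or 12; both tracers: 22 or 24.

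**Smallest Mann-Whitney p.** C(10,5) = 252 orderings without ties. With complete separation (U = 0), two-sided p = 2/252 = 0.0079; at U = 1, 4/252 = 0.0159. The Bonferroni-adjusted floor is k x 2/252.

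**t-test power.** Noncentral t, df = 8, noncentrality d x sqrt(5/2), alpha 0.05/k.

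| k | 0.05/k | Smallest adjusted Mann-Whitney p | t-test power, d = 2 |
|---|---|---|---|
| 1 | 0.0500 | 0.008 | 79% |
| 2 | 0.0250 | 0.016 | 66% |
| 3 | 0.0167 | 0.024 | 58% |
| 4 | 0.0125 | 0.032 | 52% |
| 6 | 0.0083 | 0.048 | 44% |
| 11 | 0.0045 | 0.087 | 33% |
| 12 | 0.0042 | 0.095 | 32% |

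The two-sided exact Mann-Whitney test can reach significance up to k = 6. It cannot from k = 7 (7 x 2/252 = 0.056). One-sided, the floor is k/252: 0.044 at k = 11 and 0.048 at k = 12, just reachable.

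**Other effect sizes.** At d = 3, t-test power is 98% (k = 1), 85% (k = 6) and 74% (k = 12). At d = 1 it is 29% (k = 1) and 9% (k = 6). The d needed for 80% power is 2.02 (k = 1), 2.33 (k = 2), 2.83 (k = 6) and 3.17 (k = 12).

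**Exact or approximate Mann-Whitney.** At U = 0 the normal approximation gives z = 12.5/sqrt(25 x 11/12) = 2.611, p = 0.0090 (0.0122 with continuity correction). At k = 6 the adjusted floor is then 0.054 (0.073) instead of 0.048, so the version of the test also matters.

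**Holm against Bonferroni.** Simulated multivariate normal data, 5 v 5, all outcomes at d = 2, within-tracer correlation 0.5 to 0.8 (assumed), t-test power for one named outcome. Two outcomes: 66% with Bonferroni, 72% to 74% with Holm. Four outcomes over both tracers: 52% against about 65%.

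**The case against.** The strongest reply is that this is a poor label on a sound idea. Two tracers and two outcomes are tested, correcting for that is legitimate, and Bonferroni is a valid way to do it. The study is an exploratory proof of principle with no sample size calculation. Much of this stands: loose wording is the likeliest explanation, and on that reading significance stays reachable. What remains is that the family is unlisted and k could be 2, 3, 4 or 6, a spread of 66% to 44% in power at d = 2.

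Four stronger readings should be set aside.

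- **That the plan makes significance impossible.** This needs correction over the sampling times, Mann-Whitney instead of the t-test, two-sided testing and alpha 0.05, all at once. Section 10.1 plans no test at single times and equally allows the t-test. The hypothesis in Section 1 is directional, and a one-sided test is just reachable at k = 12.
- **That the correction is stated to apply to peak height.** This can be inferred only from the order of the sentences.
- **That Section 4d would misread a null result.** It begins "In case the number of 5 subjects per group is insufficient to detect a statistical difference" and says only that the data can then be used to size a second study. It does not interpret a non-significant result, and sizing a later study is not harmed.
- **That the correction is what chiefly limits the study.** At d = 1 power is 29% with no correction at all.

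It is also fair to object that one value per volunteer presupposes a rule for combining the two samples taken at each time, and the plan gives none. That is a separate gap; the outcome remains one derived number per person.

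**Conclusion.** The point holds in a limited form. The correction as worded corresponds to no comparison in Section 10, and its family, k, alpha and sidedness are missing, so the primary analysis cannot be carried out without a guess. The consequence is lost power of uncertain size; an over-wide correction does not inflate false positives. With two-sided alpha 0.05 and d = 2 assumed, plausible families take t-test power from 79% uncorrected to between 66% and 44%. The literal time-point reading (32% at k = 12, and out of reach for a two-sided exact Mann-Whitney test) is a possibility that the wording leaves open, not what the plan prescribes. Five volunteers per group remain the main constraint. It should be fixed because the remedy is small and Holm gives the same familywise control as Bonferroni over the same family without ever being less powerful.

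**What to change.** Replace the correction sentence in Section 10.1 with:

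*Each outcome is one value per volunteer and is compared once per tracer, intervention versus control, at two-sided alpha 0.05, with Holm correction over the comparisons listed here. When the Mann-Whitney test is chosen, its exact version is used. No tests are done, or corrected for, at single breath-test times.*

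Then list the comparisons. If the sponsor keeps Bonferroni, the minimum is the list, k, alpha and sidedness.

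The sponsor has one real choice, the scope of the family:

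- **Within each tracer.** The first Holm step is 0.025 for two outcomes or 0.0167 for three; without ties, U = 0 or 1 (0.0079 or 0.0159) meets both. The chance of any false positive across both tracers is up to 1 - 0.95^2 = 9.75%.
- **Across both tracers.** Error is controlled overall, but the first step is 0.0125 (four comparisons) or 0.0083 (six), which the exact 5 v 5 Mann-Whitney test meets only with complete separation (0.0079).

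If time to peak is added because the objective names it, it joins the list. It takes only sampled times, so ties between groups are possible. With two volunteers from one group and one from the other sharing a time, its floor is 0.0238, above a first step of 0.0167. It could then pass only after another outcome had been rejected.

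Losses without replacement also matter: the floor is 2/126 = 0.0159 at 4 v 5 and 2/70 = 0.0286 at 4 v 4, and the latter misses every first step above.

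The cost is one sentence and a short list, with no new data. If a favourable opinion has already been given, the change is an amendment to notify under Section 12.3. The rule for choosing between t-test and Mann-Whitney is still missing and is not settled by this change.
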